## **2.3 SECONDARY ENDPOINTS**

The secondary endpoints will provide:

1. The occurrence of procedure-related MAEs reported as percentage of subjects with MAE, at 30-days, 9-months, 12-months, 24-months, and 36-months.  
Inclusive of:
  - a. Procedure-or device-related occurrence of death
  - b. Q-Wave MI
  - c. Clinically driven TLR
  - d. Significant embolic events
    - i. Defined as unanticipated kidney/bowel infarct clinically driven by symptoms of abdominal or back pain and confirmed with CT scan or open surgery, lower extremity ulceration or gangrene, or kidney failure after 30-days, 9-months, 12-months, 24-months, and 36-months.
2. Technical success defined as successful delivery and deployment of the iCAST™ RX Stent System with  $\leq 30\%$  residual angiographic stenosis after covered stent deployment (including post-dilatation) assessed via QVA by an independent core laboratory.
3. Procedural success defined as technical success without the occurrence of MAE prior to hospital discharge.
4. TLR measured as the proportion of subjects that require a clinically-driven reintervention of the target lesion through 9-months.
  - a. A clinically-driven TLR is defined as a TLR (PTA, bare metal stent or repeat covered stent deployment, or surgical bypass) due to documented recurrent hypertension from 30-days post-procedure level and/or deterioration in renal function from baseline value, associated with angiographic core laboratory adjudication of a  $\geq 60\%$  diameter covered stent restenosis.
5. Rate of incidental TLR defined as rate of TLRs not meeting the definition of a

clinically driven TLR.

6. Improved SBP control assessed at 30-days, 9-months, 12-months, 24-months and 36-months.
7. Secondary patency rate at 9-months after a clinically-driven TLR which restores patency after total occlusion.
8. Change in number and dosage of anti-hypertensive medications as compared to baseline.
9. Renal function compared to baseline as measured by eGFR at 30-days and 9-months.

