#### 5.3.6.2 SECONDARY ENDPOINTS ANALYSIS

##### 5.3.6.2.1 MAJOR SECONDARY ENDPOINTS

###### 5.3.6.2.1.1 TLR

The secondary endpoint of clinically driven TLR will be summarized using counts and frequencies. An exact one-sided 95% confidence interval will be

constructed and the upper limit compared to the Performance Goal rate of 8.5% as described below. A p-value for the one-sided test of the difference between the observed rate and the Performance Goal will be presented.

The Performance Goal of 8.5% was established from a review of the relevant literature as detailed in the following table.

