**Table 4: Derivation of TLR Performance Goal**

Author	# subjects	f/u time	TLR Assessment	Subjects with TLR	TLR
Rocha -Singh et al 	208	9 mo	9 mo	9	4.3%
Laird et al 	188	9-12 mo	9 mo	17	9.0%
Corriere et al 	91	12 mo	6 mo	10	11.0%
Rocha-Singh et al 	100	9 mo	9 mo	8	8.0%
Nolan et al 	78	12 mo	12 mo	8	10.3%
Nolan et al 	82	12 mo	12 mo	8	9.8%
Sapoval et al 	52	6 mo	6 mo	4	7.7%
Symonides et al 	27	6 mo	6 mo	8	29.6%
Van de Ven et al 	42	6 mo	6 mo	0	0.0%
Hennequin et al 	21	12 mo	9 mo	4	5.3%
			Weighted Average		8.5%

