SIGNIFICANT EMBOLIC EVENTS	Unanticipated kidney/bowel infarct clinically driven by symptoms of abdominal or back pain and confirmed with CT scan or open surgery, lower extremity ulceration or gangrene, or kidney failure.
STENT THROMBOSIS	Angiographic thrombus or sub-acute closure within the stented vessel.
SYSTOLIC HEART FAILURE	Heart failure with ejection fraction < 30% and/or hospitalization requiring intubation and ventilation support for this diagnosis within the previous 90 days.
TARGET LESION REVASCULARIZATION	Clinically-Driven TLR - TLR (percutaneous balloon angioplasty (PTA), bare metal stent or repeat covered stent deployment) due to documented recurrent hypertension from 30 days post-procedure level and/or deterioration in renal function from baseline value associated with angiographic core laboratory adjudication of a $\geq$ 60% diameter covered stent restenosis.  Incidental TLR – TLR not meeting the definition of a clinically driven TLR.

TECHNICAL SUCCESS	Successful delivery and deployment of the iCAST™ RX Stent System with ≤ 30% residual stenosis after stent deployment (including post-dilatation) assessed via quantitative vascular analysis (QVA) by an independent core laboratory.
TRANSIENT ISCHEMIC ATTACK	An attack where a person has stroke-like (“mini-stroke”) symptoms for up to 1 - 2 hours; these attacks are often considered a warning sign that a true stroke may happen in the future if something is not done to prevent it.
TOTAL OCCLUSION	A complete obstruction or a closure of a passageway or vessel.
UNANTICIPATED ADVERSE DEVICE EFFECT	Any serious adverse effect on health or safety, or any life-threatening problem or death caused by, or associated with, a device, if that effect, problem, or death was not previously identified in nature, severity, or degree of incidence in the Investigational Plan or IFU, or any other unanticipated serious problem associated with a device that relates to the rights, safety, or welfare of subjects.
UNANTICIPATED KIDNEY/BOWEL INFARCT	Clinically driven by symptoms of abdominal or back pain and confirmed with CT scan or open surgery.

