A clinically-driven TLR is defined as a target lesion revascularization (PTA, bare metal stent or repeat covered stent deployment, or surgical bypass) due to documented recurrent hypertension from 30-days post-procedure level and/or deterioration in renal function from baseline value, and associated with angiographic core laboratory adjudication of a $\geq 60\%$ diameter covered stent restenosis.

The percentage of TLRs will be derived as the number of subject-lesions that require a clinically-driven re-intervention divided by the number of subject-lesions in the ITT population.

5. Rate of incidental TLR

The rate of TLRs not meeting the definition of a clinically-driven TLR will be derived as the number of observed non-clinically driven TLRs divided by the total number of subject-lesions in the ITT population.

6. Improved SBP control assessed at 30-days, 9-months, 12-months, 24-months and 36-months.

The change from baseline in systolic blood pressure (SBP) at each follow-up time point will be computed as follows:

$$\text{SBP change from baseline} = (\text{SBP value at follow-up} - \text{SBP value at baseline})$$

7. Secondary patency rate at 9-months

Secondary patency rate at 9-months after a clinically-driven TLR which restores patency after total occlusion. For each subject-lesion, an indicator variable will be derived which identifies if the lesion meets secondary patency. The incidence of secondary of patency at 9 months will be computed as the number of subject-lesions that met secondary patency divided by the number of subject-lesions for the ITT population.

Confidential

8. Change in number and dosage of anti-hypertensive medications

Anti-hypertensive medications as well as the dosage will be recorded at baseline and throughout the study follow-up. The total number of anti-hypertensive medications will be computed as the sum of all available anti-hypertensive medications at each time point. Change from baseline will be computed as follows:

Change from baseline in the number of antihypertensive medications = (number of anti-hypertensive medications at follow-up – the number of anti-hypertensive medications at baseline)

Additionally, an indicator variable which detects if an increase in the number of antihypertensive medications (change from baseline > 0) was observed will be derived.

Similarly, the change from baseline in the anti-hypertensive medication dosage (within the same medication) will be computed as follows:

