9.10.1. TLR

The secondary endpoint of clinically driven TLR will be summarized using counts and frequencies. An exact binomial one-sided 95% confidence interval will be constructed and the upper limit compared to the Performance Goal rate of 8.5%. A p-value for the one-sided test of the difference between the observed rate and the Performance Goal will be presented.

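### Clinically driven TLR is compared with an 8.5% goal whose source table states no such restriction, so the documents do not show that the two events match

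*Protocol*

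**What the plan says.** Protocol 2.3, item 4, defines the endpoint as "TLR measured as the proportion of subjects that require a clinically-driven reintervention of the target lesion through 9-months". A TLR is clinically driven only if it is "due to documented recurrent hypertension from 30-days post-procedure level and/or deterioration in renal function from baseline value" and the angiographic core laboratory also adjudicates a restenosis of at least 60%. Protocol Appendix 2 defines incidental TLR as the remainder: "TLR not meeting the definition of a clinically driven TLR".

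Protocol 5.3.6.2.1.1 takes the clinically driven part alone to the goal: "The secondary endpoint of clinically driven TLR will be summarized using counts and frequencies", followed by an exact one-sided 95% limit and a p-value against 8.5%. SAP 9.10.1 keeps this: "An exact binomial one-sided 95% confidence interval will be constructed and the upper limit compared to the Performance Goal rate of 8.5" per cent, again with a one-sided p-value.

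The goal comes from Protocol Table 4. Its event column is headed "Subjects with TLR". Neither the table nor the sentence introducing it mentions a clinical driver or core-laboratory adjudication.

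Incidental TLR is reported as its own rate. SAP 7.6.2, item 5, says: "The rate of TLRs not meeting the definition of a clinically-driven TLR will be derived as the number of observed non-clinically driven TLRs", divided by all subject-lesions in the ITT population. It has no comparator.

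**The concern.** A performance goal is only as good as the match between the event counted in the trial and the event counted in the literature. Here the trial's event carries two conditions, and the benchmark, as documented, carries neither. Any re-intervention the trial files as incidental leaves its own rate. Nothing shows that the same kind of event was left out of the 8.5%.

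Incidental TLR can plausibly occur in this trial. Every subject has a scheduled duplex ultrasound at 9 months, with angiography if it suggests at least 60% stenosis (Protocol 4.5.3). Restenosis can therefore be found, and treated, without recurrent hypertension or loss of renal function.

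At stake is how the TLR result is read. A device with the same total TLR as the literature could show a limit below 8.5% because part of its re-interventions were classified out of the comparison.

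**Working it through.** **1. Reproduce the goal.** Inputs are the ten rows of Protocol Table 4.

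- Subjects: 208 + 188 + 91 + 100 + 78 + 82 + 52 + 27 + 42 + 21 = 889.
- Subjects with TLR: 9 + 17 + 10 + 8 + 8 + 8 + 4 + 8 + 0 + 4 = 76.
- Pooled rate: 76/889 = 8.55%, in line with the stated 8.5%.

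Weighting the printed percentages by subjects gives 8.2% instead. The difference comes from the last row, which prints 5.3% although 4/21 = 19.0%. The goal therefore rests on the event counts, and the definition behind those counts is what matters.

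**2. The passing rule.** The one-sided 95% exact upper limit is below 8.5% when P(X ≤ x | n, 0.085) < 0.05.

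- n = 68 (enrolled, SAP 6.1): 1 event gives probability 0.0174 and upper limit 6.8%; 2 events give 0.064 and 9.0%. At most 1 event passes.
- n = 125 (planned evaluable, Protocol 5.2): 5 events give 0.0403 and 8.2%; 6 events give 0.086 and 9.3%. At most 5 events pass.

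**3. Effect of a mismatch.** Assume that total TLR on the device is exactly 8.5%, that the 8.5% goal is a total TLR rate, and that a share s of the device's TLRs is incidental. The tested rate is then 8.5% × (1 − s). The documents give no value for s, so a range is shown.

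| s | Tested rate | Chance of passing, n = 68 (≤ 1 event) | Chance of passing, n = 125 (≤ 5 events) |
|---|---|---|---|
| 0% | 8.50% | 1.7% | 4.0% |
| 10% | 7.65% | 3.0% | 7.7% |
| 20% | 6.80% | 5.0% | 14.0% |
| 30% | 5.95% | 8.2% | 24.0% |
| 40% | 5.10% | 13.2% | 38.2% |

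At 68 subjects the exact rule is conservative (1.7% at s = 0), so the chance passes 5% only when more than about a fifth of TLRs are incidental.

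**4. The same point from the goal's side.** If a share s of the 76 literature events would be incidental under the trial's definition, the like-for-like goal is 8.55% × (1 − s): 7.7% at 10%, 6.8% at 20%, 6.0% at 30%. At n = 125 the largest passing count falls from 5 to 4, 3 and 2.

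**The case against.** **The column label may be shorthand.** The documents often write TLR when they mean clinically driven TLR: Protocol 2.3 item 4, the headings of Protocol 5.3.6.2.1.1 and SAP 9.10.1, and the TLR percentage in SAP 7.6.2 item 4 all do so. Table 4 sits inside such a section. A reader might infer from its label that the comparator is all TLR and that the comparison is therefore biased. The documents do not establish that. They show only that the definition extracted for Table 4 is not stated, and if every source count was clinically driven there is no bias. This stands, and it limits the point to an undocumented match. It does not remove it. For the patency goal, Protocol 5.2.1 lists the restenosis definition among the extracted items and names out-of-design definitions as a reason for exclusion; no such step is described for TLR.

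**No controlled error is left to inflate.** Protocol 5.3.4 made clinically driven TLR the first secondary test after the primary objective, so a reader might infer a loss of Type I error control. The SAP does not support that reading. Sections 2 and 6.2 make all inference descriptive, 8.7 drops Type I error control, and 9.10 drops the hierarchy. This stands too. What remains is interpretive: SAP 9.10.1 still sets the limit against 8.5% and reports a p-value.

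**Total re-intervention is not hidden.** Incidental TLR is a planned rate on the same denominator as clinically driven TLR, and SAP 9.11.11 summarises all additional treatment of the target vessel. That is true, but neither is compared with 8.5%, and the latter concerns the vessel rather than the lesion.

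**Replacing the endpoint would overreach.** Swapping the prespecified comparison for total TLR after enrolment has closed could create the opposite mismatch if Table 4 was restricted. This stands, and it is why the fix adds a row and replaces nothing.

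**Conclusion.** The point holds as a documentation gap with a known direction and an unknown size. Clinically driven TLR is compared with a figure whose event definition is not stated. If any Table 4 events would be incidental under the trial's definition, the comparison favours the device; if none would be, it is fair.

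At the 68 enrolled the effect is modest: a chance of passing of 1.7% to 13% for an assumed incidental share of 0 to 40%, and no more than 5% up to a share of about 20%. The 4.0% to 38% range belongs to the planned 125, which enrolment did not reach. Both ranges assume a true total TLR of exactly 8.5%, an unrestricted goal and a binomial count per subject. Since inference is now descriptive, the consequence is a possibly over-favourable reading of one secondary result. That still justifies a correction this cheap.

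**What to change.** In SAP 9.10.1:

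- Keep the prespecified clinically driven TLR row.
- Add a row for total TLR (clinically driven plus incidental) through 9 months, with its exact one-sided 95% upper limit against 8.5%. Count it per subject, as Table 4 and Protocol 2.3 item 4 do; SAP 7.6.2 divides by subject-lesions.
- State which TLR definition was extracted for Table 4, or that it is not known.
- State that the clinically driven rate will not be read as meeting the goal unless Table 4 is confirmed, or re-extracted, as clinically driven counts.

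The cost is one table row from data already collected and a few sentences of SAP text; re-extracting Table 4 from its ten sources is optional extra work. The downside is that the total rate can only be equal to or higher than the clinically driven rate, so the result may look less favourable. If Table 4 was in fact restricted to clinically driven events, the added row is conservative and should be labelled so.

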**Table 4: Derivation of TLR Performance Goal**

Author	# subjects	f/u time	TLR Assessment	Subjects with TLR	TLR
Rocha -Singh et al 	208	9 mo	9 mo	9	4.3%
Laird et al 	188	9-12 mo	9 mo	17	9.0%
Corriere et al 	91	12 mo	6 mo	10	11.0%
Rocha-Singh et al 	100	9 mo	9 mo	8	8.0%
Nolan et al 	78	12 mo	12 mo	8	10.3%
Nolan et al 	82	12 mo	12 mo	8	9.8%
Sapoval et al 	52	6 mo	6 mo	4	7.7%
Symonides et al 	27	6 mo	6 mo	8	29.6%
Van de Ven et al 	42	6 mo	6 mo	0	0.0%
Hennequin et al 	21	12 mo	9 mo	4	5.3%
			Weighted Average		8.5%

#### 5.3.6.2.1.2 CHANGES IN THE NUMBER OR DOSAGE OF ANTI-HYPERTENSIVE MEDICATIONS

The secondary endpoint of changes in the number or dosage of anti-hypertensive medications as compared to baseline will be summarized using a shift table. The number of patients will be compared to baseline using the paired McNemar's test.

#### 5.3.6.2.2 OTHER SECONDARY ENDPOINTS

All other secondary endpoints will be evaluated in the ITT population using descriptive statistics. No formal hypothesis testing will be performed. The secondary endpoints will be summarized for continuous, categorical or time-to-event data, as appropriate.

#### 5.3.6.3 SUBJECT DISPOSITION, DEMOGRAPHICS AND OTHER BASELINE CHARACTERISTICS

Baseline demographic and clinical variables will be summarized for both the ITT and Per Protocol analysis sets for continuous or categorical variables, as appropriate.

#### 5.3.6.4 SITE-LEVEL POOLABILITY

Poolability of the data across sites will be examined by testing the homogeneity of the primary endpoint results across sites using a random effects model. If differences in the primary or major secondary endpoints exist, these effects will be further examined and results will be additionally reported by adjusting for site using a random effects

model. Since there may be few patients per site and regional differences are expected, this analysis will be repeated for regional differences (US versus OUS). If heterogeneity is detected and the differences between the sites or regions can be attributed to specific differences in baseline characteristics, the random effects model will be further adjusted by these variables. Testing will be conducted at the alpha=0.15 level for this analysis.

#### 5.3.6.5 OTHER SAFETY DATA

Concomitant medications and AEs will be summarized at each follow-up visit. In addition, tables and listings will be provided.

## 6.0 ADVERSE EVENTS, SERIOUS ADVERSE EVENTS, AND UNEXPECTED DEVICE EFFECTS

In this trial, subjects should be encouraged to report AEs spontaneously or in response to general, non-directed questioning. At any time during the trial, the subject may volunteer information that identifies an AE. If it is determined that an AE has occurred, the investigator should obtain all the information required to complete the AE on the designated eCRF.

### 6.1 DEFINITIONS

Adverse Events (AE): Any untoward medical occurrence observed in a patient or a clinical investigation subject administered an investigational product and that does not necessarily have a causal relationship with this treatment. An AE can therefore be any unfavorable and unintended sign (including any clinically significant abnormal laboratory finding), symptom, or disease temporally associated with the investigational intervention, whether or not considered related to the investigational intervention. Pre-existing conditions, which worsen during a trial, are to be considered AEs.

Serious Adverse Event (SAE): Any adverse experience that results in any of the following outcomes:

- Death
- Is life-threatening
- Subject hospitalization or prolongation of existing hospitalization
- A persistent or significant disability or incapacity
- Congenital anomaly or birth defect
- Important medical events that may not be immediately life-threatening or result in death or hospitalization, but may jeopardize the subject or may require intervention to prevent one of the outcomes listed in the definition above.

Unanticipated Adverse Device Effect (UADE): Any serious adverse effect on health or safety, or any life-threatening problem or death caused by, or associated with, a device, if that effect,

problem, or death was not previously identified in nature, severity, or degree of incidence in the Investigational Plan or IFU, or any other unanticipated serious problem associated with a device that relates to the rights, safety, or welfare of subjects. A list of anticipated AEs is provided below.

#### 6.1.1 ANTICIPATED AEs

Based on the literature and on clinical and commercial experience with implantation of a covered stent in human arteries, Table 5: Anticipated AEs, includes anticipated AEs that have been identified as possible complications:

**Table 5: Anticipated AEs**

 Abdominal Pain

 Abscess

 Acute or sub-acute thrombosis

 Acute myocardial infarction

 Allergic reaction to stainless steel, drugs, contrast agent, or anti-platelet agents

 Aneurysm

 Arrhythmias, including Ventricular Fibrillation (VF) and Ventricular Tachycardia (VT)

 Arteriovenous (AV) fistula

 Bowel infarct

 Death

 Dialysis

 Emboli (air, tissue, or thrombotic) resulting in tissue ischemia or infarction

 Emergency surgery to correct vascular complications

 Extremity ischemia/amputation

 Fever

 Hemorrhage

 Hematoma

	

 Hypotension or hypertension

 Inadequate implantation or Intimal trauma

 Inadvertent exclusion of branch or accessory vessel

 Incision site pain or infection

 Injury, dissection, perforation, or rupture of the vessel

 Kidney infarct

 Myocardial infarction or ischemia

 Nephrectomy

 Pseudo-aneurysm formation

 Pyrogenic reaction

 Renal insufficiency or failure

 Restenosis of stented lesion

 Sepsis/infection

 Stent embolization

 Stent migration/stent misplacement

 Stroke or other cerebrovascular accident

 Thromboembolic event

 Tissue necrosis or ulceration

 Total occlusion

 Vessel spasm

---	---

## 6.2 DEVICE FAILURES, MALFUNCTIONS AND NEAR INCIDENTS

Investigators are instructed to report all possible device failures, malfunctions or near incidents observed during the course of the trial, to Atrium. In addition, these incidents will be documented in the eCRF provided as follows:

- Device Failure: A device failure has occurred when the device is used in compliance with the IFU, but does not perform as described in the IFU and also negatively impacts treatment of the trial subject.

- Device Malfunction: A device malfunction occurs when an unexpected change to the device that is contradictory to the IFU is observed, which may or may not affect device performance.
- Device Misuse: Any use of the investigational device by an investigator that is contradictory to the application described in the IFU will be categorized as device misuse.

### 6.3 DOCUMENTATION

All AEs must be listed in the subject's source record, transcribed onto on the appropriate eCRF, and will be characterized by the following criteria:

- Intensity or Severity
- Relatedness
- Outcome
- Treatment or Action Taken
- Expectedness

All AEs (serious and non-serious) will be recorded upon completion of the ICF process through the 9-month follow-up visit. Thereafter, only SAEs (for example, those that result in hospitalization, permanent disability, death, or threat of death) will be recorded. All SAEs will be reported to the CEC and DSMB.

#### 6.3.1 INTENSITY OR SEVERITY

The severity of the AE or SAE should be based on the following categories:

- Mild: An AE that is noticeable to the subject and may require additional therapy and is resolved without treatment and with no sequelae.
- Moderate: An AE that interferes with the subject's activities and requires intervention or additional therapies.
- Severe: An AE that is intolerable, or necessitates additional therapy or places the subject at immediate risk of harm.

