### 6.3.4 TREATMENT OR ACTION TAKEN

AEs or SAEs will result in:

- Interventional Treatment: Surgical, percutaneous or other procedure.
- Medical Treatment: Medication dose reduction/interruption or discontinuation, or medication initiated for event.
- None: No action is taken.

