9.11.2. Serious Adverse Events (SAE)

Any adverse experience that results in any of the following outcomes:

- Death
- Is life-threatening
- Subject hospitalization or prolongation of existing hospitalization
- A persistent or significant disability or incapacity
- Congenital anomaly or birth defect
- Important medical events that may not be immediately life-threatening or result in death or hospitalization, but may jeopardize the subject or may require intervention to prevent one of the outcomes listed in the definition above.

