Adverse event data summaries will be presented by System Organ Class (SOC) and Preferred Term (PT). AEs will be summarized using discrete summary statistics at the subject and event level by SOC and PT. If a subject reports the same PT multiple times within the same SOC, that PT will only be reported once within that SOC. As with the PT, if a subject reports multiple conditions within the same SOC, that SOC will only be reported once.

To count the number of subjects with any AEs, if a subject has multiple AEs coded to the same PT within the same SOC, the subject will be summarized within the maximal severity. For the summary of maximal severity, if the subject has multiple AEs of the same PT and of different grades of severity, the maximal severity will be reported. In the summary, SOC will be listed in ascending alphabetical order; PTs will be listed in order of descending frequency for all subjects within each SOC.

Separate summaries of the AEs stratified by before or after study procedure will be provided for the following categories:

- Adverse Events (AE)
- Procedure-Related AEs
- Unanticipated Adverse Device Effects (UADEs)
- Serious AEs (SAE)
- Serious Procedure Related AEs (separate for CEC adjudicated events and Investigator)
- Fatal AEs

All AEs will be presented in a subject listing. In addition, UADEs will be provided in a
Amendment #1: 15Jul13

separate listing.

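### Moderate and Severe adverse-event grades overlap when additional therapy is needed, and Mild contradicts itself, so the Moderate/Severe split in the maximal-severity summary is unreliable

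*Protocol*

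**What the plan says.** Protocol 6.3.1 applies one scale to serious and non-serious events: "The severity of the AE or SAE should be based on the following categories". It has three grades:

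- The lowest grade reads "Mild: An AE that is noticeable to the subject and may require additional therapy and is resolved without treatment and with no sequelae", so all of its conditions apply jointly.
- The middle grade reads "Moderate: An AE that interferes with the subject's activities and requires intervention or additional therapies", which is again a joint condition.
- The highest grade reads "Severe: An AE that is intolerable, or necessitates additional therapy or places the subject at immediate risk of harm", where any one of three conditions is enough.

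The section has no rule for an event that fits more than one grade, or none.

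SAP 9.11.4 uses these grades when it counts subjects. Within a preferred term, "if the subject has multiple AEs of the same PT and of different grades of severity, the maximal severity will be reported". The SAP does not restate or refine the definitions.

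Two neighbouring attributes are recorded separately. Protocol 6.3.4 captures the action taken as interventional treatment, medical treatment or none. Seriousness is defined by outcome (Protocol 6.1; SAP 9.11.2), without reference to the grade.

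**The concern.** A severity scale should give each event one grade, and two careful graders should reach the same one. Here therapy appears in all three grades and does a different job in each. In Severe it is sufficient alone. In Moderate it is one half of a joint condition. In Mild it is permitted and then contradicted.

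Consider an activity-limiting, non-serious event that is treated with one added drug. A site reading Severe literally records Severe. A site reading for the evident intent records Moderate. Both can point to the text. Because the SAP keeps the maximum within a preferred term, one event graded upward sets that subject's entry.

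The trial is single-arm and open-label (SAP 5.3, 5.4), so there is no comparator graded under the same wording to offset the effect. With 68 subjects enrolled (SAP 6.1), a few discordant grades could visibly change a severity display.

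**Working it through.** No power, rate or sample size is involved, and the plan gives no figure to reproduce. The check is a logical one.

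**Inputs.** The definitions in Protocol 6.3.1, coded on seven yes/no attributes: needs additional therapy (T), needs intervention (I), interferes with activities (A), intolerable (X), immediate risk of harm (R), resolved without treatment (U), no sequelae (S). Noticeable is taken as true throughout.

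| Grade | Condition as written |
|---|---|
| Mild | U and S (therapy only a possibility) |
| Moderate | A and (I or T) |
| Severe | X or T or R |

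**Step 1: profiles.** Seven attributes give 2^7 = 128 profiles. The loose reading allows all of them. The strict reading treats U as incompatible with T or I. Of the 64 profiles with U, three quarters (48) also have T or I, so 128 − 48 = 80 remain.

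**Step 2: events needing additional therapy (T = 1).**

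| | Strict | Loose |
|---|---|---|
| Profiles | 2^5 = 32 | 2^6 = 64 |
| Meet Severe | 32 | 64 |
| Also meet Moderate (A = 1) | 16 | 32 |
| Also meet Mild (U = S = 1) | 0 | 16 |
| Meet all three | 0 | 8 |

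On both readings, every such profile is Severe and half are also Moderate. So every event that is Moderate through additional therapy is also Severe. Moderate is distinct from Severe only when an event needs an intervention that is not additional therapy and is neither intolerable nor an immediate risk.

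**Step 3: events not needing additional therapy (T = 0).** These number 80 − 32 = 48 (strict) or 128 − 64 = 64 (loose). Of these, 8 and 9 respectively fit no grade. One example limits activities, resolves untreated with sequelae, and is neither intolerable nor an immediate risk. On the strict reading, 6 of the 48 meet both Moderate and Severe and 6 meet both Mild and Severe, because neither lower grade excludes an intolerable event or one posing immediate risk. A highest-grade rule would settle these 12, but none is stated.

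**Step 4: Mild.** An event that needs therapy and resolves without treatment exists only on the loose reading. On the strict reading, the therapy clause in Mild describes no event.

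These are counts of logical profiles. They show where the wording overlaps or leaves gaps and say nothing about how often such events occur.

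**The case against.** The strongest reply is that little depends on the grade. The main safety outcome is the incidence of subjects with any AE after the procedure (SAP 7.6.3). The separate summaries listed in SAP 9.11.4 cover AEs, procedure-related AEs, unanticipated device effects, serious events, serious procedure-related events and fatal events. None is defined by severity, no primary or secondary endpoint uses it, and the SAP already treats inferential results as descriptive. All of this stands and keeps the point minor.

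A reader might also infer four stronger claims, which the documents do not support.

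- *A treated event meets all three grades alike.* Mild also requires resolution without treatment and no sequelae, and Moderate also requires interference with activities. Strictly, 0 of 32 profiles needing therapy meet Mild. Even on the loose reading only 8 of 64 meet all three.
- *Two compliant sites could grade a treated event at opposite ends of the scale.* A treated event did not resolve untreated, so Mild is not available for it. The ambiguity for treated events is between adjacent grades.
- *Every AE that received therapy is ambiguous.* A treated event that does not limit activities is, on the strict reading, Severe only. That may be surprising, but it is not ambiguous. Action taken is also an imperfect proxy: "Medical Treatment: Medication dose reduction/interruption or discontinuation, or medication initiated for event" includes reducing or stopping a drug, which is not additional therapy.
- *The severity summary cannot be interpreted at all.* Only the Moderate/Severe split is undermined by the therapy overlap.

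Finally, a protocol edit comes late. Enrollment has ended, and non-serious events are recorded only through the 9-month visit (Protocol 6.3). This is a fair limit on rewording. It does not affect the analysis-side remedy.

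**Conclusion.** The concern holds as a minor defect. As written, Moderate and Severe overlap for any activity-limiting AE that needs additional therapy, a need for additional therapy alone makes an event Severe, and Mild contradicts itself. With no tie rule in either document, the Moderate/Severe split in the SAP's maximal-severity summary is unreliable and, on a literal reading, shifted towards Severe for treated events. The summaries of AE incidence, serious events, unanticipated device effects, procedure-related events and fatal events are unaffected.

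The size cannot be given as a number, because the documents report no events by grade or by action taken. The conclusion assumes that additional therapy means the same in all three grades and that no tie rule exists elsewhere. Form-completion guidance and the table shells are not among the documents, so neither a rule held there nor the final layout of the severity display could be checked.

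**What to change.** **Events already graded.** Keep the grade as recorded. Footnote the severity display with the Protocol 6.3.1 definitions. Add to SAP 9.11.4 a cross-table of severity by action taken (interventional, medical, none) and by seriousness. Rest safety conclusions on those two fields and not on the Moderate/Severe split. The cross-table will show how treated events were graded, with the caveat that medical action includes dose reduction and stopping.

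**Events still to be graded.** Remove therapy from all three definitions, since 6.3.4 already records it, and grade on intensity alone:

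- Mild: noticeable, with no interference with activities
- Moderate: interferes with activities
- Severe: intolerable, or immediate risk of harm

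State that the highest applicable grade is used. Also state that an event the subject does not notice, such as an abnormal laboratory finding that counts as an AE under 6.1, takes the lowest grade unless a higher one applies. The scale then depends on A, X and R only. Of the 2^3 = 8 combinations, 6 are Severe (X or R), 1 is Moderate and 1 is Mild, so each event has exactly one grade.

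Removing therapy only from Mild and Severe would not be enough. A treated event that does not limit activities, and is neither intolerable nor an immediate risk, would then have no grade.

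**Cost.** One extra table from fields already collected, one footnote and a short protocol edit. The edit reaches few events: after the 9-month visit only serious events and, per Protocol Appendix 4, unanticipated device effects are recorded. Earlier grades stay on the old scale, so the two scales must not be pooled in one maximal-severity display without a flag.
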